8.4 Definition of a Serious Adverse Event (SAE)

Title 21 of the CFR also provides a definition for serious adverse events (SAEs), described as those events that result in death; or are life-threatening; or require prolonged inpatient hospitalization or prolongation of existing hospitalization; or create persistent or significant disability/incapacity, or a congenital anomaly/birth defects. However, application of this definition is difficult in subjects who, as a result of their

underlying congenital disorder, present with life-threatening illness. Therefore, for this study, we modify the standard definition, and define **serious adverse events** as those events that:

- Result in death.
- Are life-threatening, that is, places the patient at immediate risk of death from the event as it occurred.
- Require hospitalization.
- Important medical events that may not result in death, be life-threatening, or require hospitalization may be considered serious adverse drug events when, based upon appropriate medical judgment, they may jeopardize the patient and may require medical or surgical intervention to prevent one of the outcomes listed in this definition.

Previously planned (prior to signing the ICF) surgeries should not be reported as SAEs unless the underlying medical condition has worsened during the course of the study. Elective admissions for surgeries or interventions, such as orthopedic surgeries, that are expected complications of AGS, will not be considered SAEs. Admissions for expected complications of AGS, including seizures, changes in neurologic function, interventions for tone management, interventions for feeding failure, will not be considered SAEs. All admissions associated with infection or hematologic disturbances will be reported as SAEs.

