8.4.1 Expected and Unexpected Adverse Events

An unexpected adverse event or reaction is defined as any adverse experience, the specificity or severity of which is not consistent with the risks of information described in the protocol. Expected adverse events are those that are identified in the research protocol as having been previously associated with or having the potential to arise as a consequence of participation in the study or are part of the clinical spectrum of the underlying disorder. Common acute and chronic complications of AGS include but are not limited to:

- Seizures
- Intermittent encephalopathy
- Progressive decline in neurologic function
- Skin rashes (such as chilblains) including panniculitis and secondary infections and amputations
- Large vessel central nervous system vasculitis
- Lupus like renal dysfunction
- Autoimmune hepatitis and elevation of liver enzymes and liver function tests
- Pulmonary hypertension
- Cardiomyopathy
- Myopathy
- Glaucoma
- Gastrointestinal disease with bowel inflammation
- Urinary tract infection
- Hip dislocation or scoliosis

- Chronic lung disease
- Spasticity and dystonia
- Feeding difficulties
- Thrombocytopenia
- Anemia
- Hypothyroidism
- Gastroesophageal reflux

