8.5.2 Suspected Unexpected Serious Adverse Reactions

Suspected unexpected serious adverse reactions (SUSARs) are serious events that are not listed in the Prescribing Information and that the investigator identifies as related to investigational product or procedure.

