Children with AGS are at risk of respiratory, skin and urinary tract infections as part of their disease. Unless these infections fall into the categories below, there will not be drug discontinuation for these events. Patients will receive treatment as clinically indicated for these infections. Discontinuation of baricitinib has been associated with neurologic decline in patients with AGS¹⁷, leading to greater caution around holidays from drug therapy in the context of acute infections.

Certain categories of infections will require specific management:

Serious infections are defined as those resulting in or occurring during hospitalization, or need for parenteral antimicrobial treatment. In these cases, the diagnostics and treatment plan will be discussed with local infectious disease team for decisions regarding continuation, decrease or interruption of study treatment. All events where infection is associated with hospitalization or need for parenteral antimicrobial treatment will be reported to the DSMB and IRB as a SAE within 24 hours of learning of the event. Patients will receive treatment as clinically indicated regardless of treatment decisions for baricitinib.

Disseminated/complicated herpes zoster, for which drug cessation will occur until improvement in symptomatic herpes zoster infection occurs (resolution of PCR positive serologies or all lesions crusted) as confirmed by local infectious disease team. Disseminated/complicated herpes zoster is defined as multidermatomal involvement in cases of reactivation, central nervous system involvement or systemic involvement including hepatitis or pneumonitis). After improvement, baricitinib may be resumed. Herpes zoster that is not confirmed, is self resolving, limited to skin without CNS, hepatic or pulmonary involvement, will result in discussion with local infectious disease team but will not result in immediate drug discontinuation. The infection will be managed as clinically indicated. Patients will receive treatment as clinically indicated regardless of treatment decisions for baricitinib. All events of disseminated/complicated herpes zoster will be reported to the DSMB and IRB within 24 hours of learning of the event as a reportable event.

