9.4.2.1.5 Thrombosis

Thrombosis, including deep venous thrombosis (DVT) and pulmonary embolism (PE), has been observed at an increased incidence in adult patients treated with baricitinib compared to placebo. In addition, arterial thrombosis events in the extremities have been reported in clinical studies with baricitinib. Many of these adverse events were

serious and some resulted in death. There was no clear relationship between platelet count elevations and thrombotic events. As of March 2020, in one patient with AGS, thrombosis of the pulmonary vasculature, associated with previously unrecognized severe pulmonary hypertension, caused death. Thus, baricitinib should be used with caution in patients who may be at increased risk of thrombosis, and in particular in AGS patients with underlying pulmonary hypertension. In AGS, regular screenings for pulmonary hypertension will occur according to clinical recommendations. If clinical features of DVT/PE or arterial thrombosis occur, patients should be evaluated promptly and treated appropriately.

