9.4.2.2.4 Liver Enzyme Elevations

Treatment with baricitinib was associated with increased incidence of liver enzyme elevation compared to placebo. Increases to greater than or equal to 5x and greater than or equal to 10x upper limit of normal (ULN) were observed for both ALT and AST in adult patients in baricitinib clinical trials. Additionally, without treatment, increases of both ALT and AST are seen in one-third of individuals affected by AGS. Liver function and enzyme testing will be checked in individuals with ongoing treatment with baricitinib according to the study schedule and management of laboratory abnormalities will be performed according to Appendix 9. Discussion with the study staff will help to determine if this complication is caused by AGS (see Appendix 9 for guidance).

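### Section 8.4 drops three seriousness criteria it recites and exempts admissions for AGS complications whatever their link to baricitinib or its withdrawal, so some related non-fatal harms can miss SAE status

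*Combined protocol and SAP*

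**What the plan says.** Section 8.4 first recites the regulatory criteria. Besides death and life-threatening events, they cover events that "require prolonged inpatient hospitalization or prolongation of existing hospitalization; or create persistent or significant disability/incapacity, or a congenital anomaly/birth defects". It says this definition is hard to apply to patients whose disease itself brings life-threatening illness, and replaces it with four items: death, immediate risk of death, hospitalization, and important medical events judged serious.

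The section then sets exemptions. One begins "Admissions for expected complications of AGS, including seizures, changes in neurologic function", goes on to interventions for tone and for feeding failure, and rules that such admissions are not SAEs. Admissions linked to infection or hematologic disturbance stay SAEs.

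Section 8.4.1 lists common AGS complications. Among them are progressive neurologic decline and "Autoimmune hepatitis and elevation of liver enzymes and liver function tests". Its definition of an expected event ends with the alternative "or are part of the clinical spectrum of the underlying disorder". Section 8.5.2 uses another test: SUSARs are "serious events that are not listed in the Prescribing Information" that the investigator considers related.

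Two statements in the risk sections bear on this. Section 9.4.2.1.1: "Discontinuation of baricitinib has been associated with neurologic decline in patients with AGS". Section 9.4.2.2.4: "Treatment with baricitinib was associated with increased incidence of liver enzyme elevation compared to placebo".

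**The concern.** The exemption sorts admissions by type of complication, and a suspected relationship to the drug does not bring an admission back in. Section 8.4.2 already provides a causality scale on which the underlying disease counts against a drug relationship, so attribution to AGS could be handled there. Instead, an admission can lose SAE status whatever its causality rating.

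This matters because several safeguards operate only on SAEs. The study is open-label with a single treated arm, so no concurrent control group would show an excess of admissions. The clearest gap is also in the domain of the primary endpoint: the AGS scale measures neurologic function, and neurologic change is what the exemption names.

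**Working it through.** No figure in the plan is in dispute, so the check is mainly a comparison of text.

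**1. Criteria recited against criteria adopted (8.4)**

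| Recited from Title 21 | In the trial's list? |
|---|---|
| Death | Yes |
| Life-threatening | Yes |
| Hospitalization | Yes, subject to the exemptions |
| Longer stay for a patient already admitted | No |
| Lasting or significant disability | No |
| Congenital anomaly | No |

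Six are recited and three are missing. The stated reason, life-threatening illness at presentation, bears on the second row, which is kept. It does not explain the last three.

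**2. A neurologic case taken through 8.4.** Suppose a child loses skills while baricitinib is being tapered.
- The event is neither fatal nor immediately life-threatening, so the first two items do not apply.
- If the child is admitted, a change in neurologic function is named in the exemption. The infection and hematology exception does not apply.
- If the child is not admitted, the disability criterion that would have captured the event is gone.
- The important-medical-event item remains, but it is discretionary. It also refers to preventing one of the outcomes in the trial's list, where disability no longer stands.

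The planned-surgery exemption in the same section has an exception for worsening disease. The AGS-complication exemption has none.

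**3. A liver case.** The exemption does not name liver events. They appear in the 8.4.1 list, which 8.4 does not cite. If expected complications are read through that list, a hepatitis admission is exempt; if not, it is an SAE. The wording allows either reading.

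**4. What depends on SAE status**
- Medical Monitor review of causality (8.5, 8.5.1).
- SAE reporting to the IRB, within 7 business days for events that are neither fatal nor life-threatening (8.5.1).
- The 15-day FDA report for serious, unexpected and related events (8.6).
- The study rules (8.7): one directly related SAE prompts a temporary stop; two non-fatal ones, or one related death, stop the study.
- Detailed description in the analysis (6.3.5).

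**5. What does not depend on it**
- Recording of every AE with causality (8.3).
- AE tables by severity and relationship (6.3.5).
- Aggregate reports of all AEs to the DSMB and IRB, and annually to FDA (8.5).

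**6. Illustration for the two-SAE rule.** Take n = 55 (3.2.2). Assume each subject independently has probability p of a related non-fatal SAE under the full definition, and that a share f of these is exempted and not restored by judgment. With q = p(1 − f),

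P(at least 2) = 1 − (1 − q)^n − nq(1 − q)^(n−1).

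For p = 5% and f = 0, q = 0.05: 1 − 0.95^55 − 55 × 0.05 × 0.95^54 = 76.8%. For f = 50%, q = 0.025 and the result is 40.1%.

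| p | f = 0 | 25% | 50% | 75% |
|---|---|---|---|---|
| 2% | 30.1% | 20.0% | 10.5% | 3.1% |
| 5% | 76.8% | 61.6% | 40.1% | 15.1% |
| 10% | 97.8% | 92.5% | 76.8% | 40.1% |

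With the 45 evaluable patients of section 6.4 and p = 5%, the row is 66.5%, 50.7%, 31.1%, 10.9%. Both p and f are assumptions; the documents give neither.

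**7. Unexpectedness.** Under 8.4.1 an event can be expected because it belongs to the disease. Under 8.5.2 the reference is the Prescribing Information. Section 8.6 makes expedited reporting turn on the word without saying which test applies. A related neurologic decline could be classed differently under each.

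**The case against.** The sponsor has a fair reply. The modification is stated openly, and section 8 requires final IRB approval and FDA authorization before enrollment. In a population with frequent disease-driven admissions, reporting each one as an SAE would bury the signal. Infection and hematologic admissions, a large part of the known drug risk, stay SAEs. Deaths and life-threatening events do too, and judgment can raise other events. Section 4.9 requires DSMB notice within 48 hours when dosing is reduced, interrupted or stopped for an AE or laboratory finding. Section 8.2 sends notable non-serious events to the IRB at continuing review. For liver abnormalities, 9.4.2.2.4 has study staff discuss whether AGS is the cause. Pregnancy and fetal outcomes have their own line in 8.5. All of this stands and limits the finding. None of it gives SAE status to a related neurologic admission.

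A reader might also infer more than the documents support:
- *That these harms escape FDA reporting altogether.* Only expedited reports are affected; the annual aggregate covers all AEs.
- *That pulmonary hypertension, myopathy and renal admissions are equally exposed drug risks.* The thrombosis described in 9.4.2.1.5 as "associated with previously unrecognized severe pulmonary hypertension, caused death" was fatal, so it remains an SAE, and the protocol attributes pulmonary hypertension to interferon. It reports CPK rises but names no drug myopathy. Section 9.4.2 does not list renal dysfunction as a drug risk.
- *That Table 1 measures the problem.* AST at grade 2 or higher rose from 1/35 to 5/35, but ALT fell from 2/35 to 1/35 and GGT was 9/35 before and 10/35 on study. Creatinine and eGFR had no grade 2 or higher in either period. These are maximum laboratory grades over periods of unstated length, not admissions.
- *That every disease-spectrum event is automatically expected.* Section 8.4.1 also calls an event unexpected when its specificity or severity does not fit the risks described.

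**Conclusion.** The point holds in a bounded form. Three recited criteria are absent for a reason that explains none of them, and the AGS-complication exemption takes no account of a suspected drug or withdrawal relationship. Neurologic decline is the firm case, because it is both named in the exemption and linked by the protocol to stopping baricitinib. Liver events are exposed only if the exemption is read through 8.4.1.

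The gap covers admissions that are non-fatal, non-life-threatening, non-infectious and non-hematologic, and that nobody raises as important medical events. I take the exemption to apply to the hospitalization criterion only, so that death and life-threatening events remain SAEs.

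Its size in this trial is unknown. The illustration shows how strongly a two-event rule depends on classification, but not how often misclassification would occur. Section 8.7 also speaks of events directly related to use of the drug and does not say whether a withdrawal event counts. For such events, the loss of Medical Monitor review is more certain than the loss of a stopping trigger.

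**What to change.** In 8.4, restore the three criteria: prolongation of an existing stay, persistent or significant disability, and congenital anomaly. State that the AGS-complication exemption does not apply when a relationship to baricitinib, or to its reduction or withdrawal, is rated at least possible under 8.4.2, and have the Medical Monitor review that rating. Section 8.4.2 is worded around drug administration, so add a line saying how timing relative to dose reduction or stopping is rated. State whether 8.4's expected complications means the 8.4.1 list. Reconcile 8.4.1 and 8.5.2 so that 8.6 uses one test of unexpectedness.

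The cost is an amendment and some extra SAE forms. Requiring every unplanned admission to be an SAE would be a debatable trade-off here and is not needed to close this gap. Exempted admissions rated unrelated can go to the DSMB in aggregate.

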8.4.1 Expected and Unexpected Adverse Events

An unexpected adverse event or reaction is defined as any adverse experience, the specificity or severity of which is not consistent with the risks of information described in the protocol. Expected adverse events are those that are identified in the research protocol as having been previously associated with or having the potential to arise as a consequence of participation in the study or are part of the clinical spectrum of the underlying disorder. Common acute and chronic complications of AGS include but are not limited to:

- Seizures
- Intermittent encephalopathy
- Progressive decline in neurologic function
- Skin rashes (such as chilblains) including panniculitis and secondary infections and amputations
- Large vessel central nervous system vasculitis
- Lupus like renal dysfunction
- Autoimmune hepatitis and elevation of liver enzymes and liver function tests
- Pulmonary hypertension
- Cardiomyopathy
- Myopathy
- Glaucoma
- Gastrointestinal disease with bowel inflammation
- Urinary tract infection
- Hip dislocation or scoliosis

- Chronic lung disease
- Spasticity and dystonia
- Feeding difficulties
- Thrombocytopenia
- Anemia
- Hypothyroidism
- Gastroesophageal reflux

8.4.2 Relationship of SAE to study drug or other intervention

Relationship of study drug to the adverse event or suspected adverse reaction is defined as follows:

- Unrelated: Adverse event is clearly due to extraneous causes (e.g., underlying disease)
- Unlikely related (must have 2 of the below):
 - Does not have temporal relationship to drug administration
 - Could readily have occurred due to subject's clinical state
 - Could have been due to environment or other interventions
 - Does not follow known pattern of response to drugs
 - Does not reappear or worsen with reintroduction of drug
- Possibly related (must have 2 of below):
 - Drug administration and the occurrence of the AE are reasonably related in time
 - Could not readily have occurred due to subject's clinical state
 - Could not readily be due to environment or other interventions
 - Follows a known pattern of response to drug
- Probably related (must have 3 of the below):
 - Drug administration and the occurrence of the AE are reasonably related in time
 - Could not readily have occurred due to subject's clinical state
 - Could not readily be due to environment or other interventions
 - Follows a known pattern of response to drug
- Definitely related (must have all 4 of the below):
 - Drug administration and the occurrence of the AE are reasonably related in time
 - Could not readily have occurred due to subject's clinical state
 - Could not readily be due to environment or other interventions
 - Follows a known pattern of response to drug

8.5 IRB/IEC Notification of SAEs and Other Unanticipated Problems

The study coordinator is responsible for collecting and recording all clinical and laboratory data. Adverse events will be collected on subjects at all follow ups, as well as by phone or e-mail communication with parents 4 weeks following initiation of study agent. The reporting period for new AEs is the period from the start of study drug administration until one month after cessation. Follow-up reports on AEs should continue up to 30 days after the administration of drug if the AE did not resolve. For each AE, the site investigator will assess severity, and whether the event meets the definition of a serious adverse event and will report whether baricitinib treatment was interrupted or stopped, as well as the outcome of the AE. If the event is an SAE, both the site PI and the Medical Monitor will assess the relationship to drug.

If a non-serious adverse event is unresolved at the time of assessment, the site investigator will make a clinical assessment as to whether continued follow-up of the AE is warranted, and the results of this assessment must be documented. If a non-serious adverse event is unresolved at the time of discharge from the study, the Principal Investigator and the Medical Monitor will make a joint clinical assessment as to whether continued follow-up of the AE is warranted. Resolution is defined as the return to baseline status or stabilization of the condition with the expectation that it will remain chronic.

The PI will prepare aggregate reports of all adverse events (serious/not serious and expected, unexpected) for the DSMB and the IRB as required and for the FDA on an annual basis.

Lack of drug effect is not an AE in clinical studies, because the purpose of the clinical study is to establish drug effect.

Cases of pregnancy that occur during maternal or paternal exposures to investigational product or drug-delivery system should be reported. Data on fetal outcome and breast feeding are collected for regulatory reporting and drug-safety evaluation.

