1.5 Relevant Literature and Data

AGS is a monogenic disorder resulting from loss-of-function (except in the case of IFIH1) mutations in any of several distinct genes, resulting in a type 1 interferonopathy associated with both peripheral manifestations and devastating neurologic consequences. Given that AGS is an interferon-mediated disease, patients with AGS are expected to benefit from JAK1 and JAK2 inhibition and, thus, it may be beneficial to treat them with baricitinib. The purpose of this clinical trial is to establish whether baricitinib can be effectively used to treat children affected by AGS.

Measurement of Clinical Diary Scores

[figure not shown]
As interferon levels can fluctuate daily in individuals affected by AGS, we have established a daily selfmeasure of systemic inflammation, the daily AGS symptom diary (Figure 5 and Appendices 5 and 6). This clinical diary has been in use in the Lillysponsored expanded access program for the JAK inhibitor baricitinib (**NCT01724580, JAGA**) since February 2017. As part of the protocol, each patient or patient-proxy completes a daily assessment of symptomatology. This includes a minimum of 2 weeks of baseline daily scores, daily reports while on study drug, and in the case of drug cessation, an additional 28 days of diary entries. Two forms of the

diary are offered: paper and electronic, as administered through REDCap. The diary allows for daily assessment of systemic signs of inflammation, and includes familybased assessment of irritability, skin findings, and hyperthermia (Appendices 5 and 6). The clinical diaries have shown to be responsive to baricitinib (Figure 5). The diary scores will be further validated against other outcome measures, as described below.

Measurement of IFN signaling gene scores

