4.8 Dosing changes

On occasion, if drug related adverse events are seen, changes or discontinuation of study medication will be considered. Because abrupt drug discontinuation may result in rebound inflammation, tapering of dosing to the next dosing increment (e.g. 2 mg three times a day to 2 mg twice a day – Appendix 14) may be considered in response to suspected drug related adverse events. Repeat laboratory testing will be performed after drug tapering and results will be discussed with the study team to assess that drug continuation at a lowered dose is in the best interest of the patient.

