Abbreviations: ET = early termination; HBsAg = hepatitis B surface antigen; HBcAb = hepatitis B core antibody; HBsAb = hepatitis B surface antibody; HIV = human immunodeficiency virus; SAVI = STING-associated vasculopathy with onset during infancy.

- a. Early termination visit is required if early termination occurs.
- b. Visits occur at approximately 4-week intervals during Weeks 16 through 52 (including both required and optional visits).
- c. Visits occur at approximately 12-week intervals during Weeks 60 through 288.
- d. Visit 2 encompasses the initial dosing period and can vary in time depending on whether the patient progresses through the first and second dose escalation during this period. Four days is the minimum time.
- e. Every effort should be made to schedule patient visits within the allowable visit window; however, if a patient visit is scheduled outside the visit window, it will not be considered a protocol violation.
- f. If results are available from testing within 1 month, then the patient will not have to be retested.
- g. Chest X ray will be performed on a clinical basis and results reviewed during screening. If chest x-ray was not performed clinically within 6 months prior to the study, it will be performed as part of the research study.
- h. If results are available from testing within 1 month or as part of the pre-screening period, then the patient will not have to be retested at Visit 1.
- i. At least 2 weeks of diary scores are required prior to beginning investigational product.

- j. Collect prior to each dose escalation. Investigator will review to ensure dose escalation is appropriate. Collect prior to the last dose given at Visit 2.
- k. Drug will be dispensed at visit 2, visit 204, and then every 6 months during onsite visits. However, when traveling to the investigative site is not considered safe for the patients due to unforeseeable events (see footnote o), such as public or personal health emergencies, the study drug may be dispensed for a longer time.
- I. If results are available from testing within the previous 3 months, then the patient will not have to be retested.
- m. For female patients of child-bearing potential: a serum pregnancy test will be performed at Visit 1 and a urine pregnancy test (local laboratory) will be performed at Visit 2 to determine study eligibility. At subsequent visits, a urine pregnancy test will be performed.

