- n. Baricitinib concentration samples will be collected at on-site visits. Samples will be collected after beginning baricitinib therapy and at each dose escalation, and may be collected at each study visit for safety monitoring. However, when traveling to the investigative site is not considered safe for the patients due to unforeseeable events (see footnote o), such as public or personal health emergencies, baricitinib concentration samples will not be collected.
- o. These required visits should be performed at the investigative site. However, in some circumstances, unforeseeable events, such as public health emergencies, states of emergency related to civil unrest, or weather emergencies, or individual health emergencies (affecting the patient or a caregiver), may create situations where it is unsafe for patients and their families to travel to the study site for in person assessments. In that case, the visits will be conducted using video operations. The changes from an in person evaluation, including differences to the study outcome collection, will be reported as a minor protocol deviation to the IRB at the time of continuing review.
- p. These required visits may be performed at the investigative site or as a telephone visit. If a telephone visit is performed, lab samples should be obtained locally and the required labs to be reported are: total bilirubin, direct bilirubin, alanine aminotransferase (ALT), aspartate aminotransferase (AST), blood urea nitrogen (BUN), creatinine, and all hematology. In addition, physical examination is not needed if a telephone visit is performed.
- q. Optional visits may be performed at the investigative site or as a telephone visit but will not be considered a protocol violation if not performed. If a telephone visit is performed, lab samples should be obtained locally. Optional visits between weeks 60 to 288 would only be performed to allow patients to re-align with the initial in-person versus phone visit schedule, in cases where this schedule would be disrupted by an unforeseeable event (refer to footnote "o" for examples of such events) to enhance patients safety. For instance, if a patient were not able to come on-site for several months or years, an in-person visit may be necessary for the providers to assess the patient in-person.
- r. EKG and echocardiogram will be performed on a clinical basis and reviewed during screening.

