Appendix 13. Cutaneous LE Disease Area and Severity Index (CLASI)

Appendix 14. Dose tapering guidance

The following serves as guidance for dose tapering if necessary due to subject tolerance. If dose tapering is conducted for subject preference, dose tapering may occur more slowly, as needed for subject tolerance.

in two week increment unless resolution of AE requiring tapering * smaller dose increments obtained by pill cutter, until small pill size can be provided to patient where available

Initial dose	Dose decrease 1 #	Dose decrease 2 #	Dose decrease 3 #	Dose decrease 4 #	Dose decrease 5 #
1 mg bid	1 mg am and 0.5 mg* pm	0.5 mg* bid	0.5 mg am	stop	
1 mg tid	1 mg bid	1 mg am and 0.5 mg* pm	0.5 mg* bid	0.5 mg am	stop
1 mg qid	1 mg tid	1 mg bid	1 mg am and 0.5 mg* pm	0.5 mg* bid	stop
2 mg bid	1 mg tid	1 mg bid	1 mg am and 0.5 mg* pm	0.5 mg* bid	stop
2 mg tid	2 mg bid	1 mg * tid	1 mg * bid	0.5 mg* bid	stop
2 mg qid	2 mg tid	2 mg bid	1 mg * tid	1 mg* bid	stop
3 mg bid	2 mg bid	1 mg * tid	1 mg * bid	0.5 mg* bid	stop
3-2-3 mg	2 mg tid	2 mg bid	1 mg * tid	1 mg * bid	stop
3 mg qid	3-2-3-2 mg	2 mg qid	2-1-2-1 mg	1 mg qid	stop
4 mg bid	2 mg tid	2 mg bid	1 mg * tid	1 mg* bid	stop
4-2-4 mg	2 mg* qid	2 mg tid	2 mg bid	1 mg bid	stop
5 mg bid	4 mg bid	2 mg tid	2 mg bid	1 mg bid	stop
4 mg tid	2 mg* qid	2 mg tid	2 mg bid	1 mg bid	stop
6 mg bid	5 mg bid	4 mg bid	2 mg tid	2 mg bid	stop

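### No required contact is timed to the month after the last dose: closeout Visit 801 is fixed at week 292 with conflicting status, and the early-termination visit has no interval from last dose

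*Combined protocol and SAP*

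**What the plan says.** Section 8.5 sets the AE period: "The reporting period for new AEs is the period from the start of study drug administration until one month after cessation". It describes collection this way: "Adverse events will be collected on subjects at all follow ups, as well as by phone or e-mail communication with parents 4 weeks following initiation". That extra contact follows the start of drug, and no matching contact is named after the end of drug. For unresolved events the same section says: "Follow-up reports on AEs should continue up to 30 days after the administration of drug if the AE did not resolve". Section 8.5.1 requires SAEs for 28 days after the last dose, whatever the judged cause.

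In Appendix 2, Safety Closeout Visit 801 is placed at week 292 from enrollment, with a window of 5 days either side and the AE row marked. It is listed in the Required row, yet its number carries footnote q, the same footnote that labels the Optional row: "Optional visits may be performed at the investigative site or as a telephone visit but will not be considered a protocol violation if not performed".

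For patients who leave early, footnote a says: "Early termination visit is required if early termination occurs". Section 4.9.1 gives this visit to subjects who withdraw from the study and lets it be done by telephone. The AE row is marked, but neither place gives an interval from the last dose.

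Section 3.2.1 and the starred note to Appendix 2 extend visits past week 288 for patients who cannot move to commercial supply. They give no new timing for the closeout.

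**The concern.** Section 8.5 makes a promise about a period, and Appendix 2 has to deliver it. AEs are collected at follow-up contacts, so a period without a required contact relies on families reporting unprompted.

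The protocol itself treats this period as one of risk. Section 4.8 warns that "abrupt drug discontinuation may result in rebound inflammation", and Section 9.4.2.1.1 reports an association between stopping baricitinib and neurologic decline in AGS. Section 8.4 excludes admissions for seizures and for changes in neurologic function from the SAE definition. The 28-day SAE duty may therefore not pick up the expected withdrawal harm. Ordinary AE collection has to do so, and that is the part with no contact timed to it.

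Section 6.3.5 reports AE incidence with exact binomial intervals, and Section 6.4 calls the safety analysis descriptive. The intervals allow for sampling error and not for events that were never asked about.

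**Working it through.** **Inputs.** Maximum treatment is 288 weeks (synopsis). Visit 801 is at week 292, plus or minus 5 days (Appendix 2). The AE period is one month after cessation, with unresolved AEs followed to 30 days (Section 8.5). The SAE period is 28 days (Section 8.5.1). Regular visits after week 60 are about 12 weeks apart (Appendix 2, footnote c).

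**Step 1: reproduce week 292.** 288 weeks + 28 days = 288 + 4 = week 292, an exact match. With the window, 801 falls 28 − 5 = 23 to 28 + 5 = 33 days after a stop at week 288. The visit was evidently built for that patient. Even there, the nominal day 28 precedes day 30, and an early visit at day 23 leaves the last week of the month uncovered.

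**Step 2: which stopping dates does 801 serve?** Week 292 is day 292 × 7 = 2,044. For 801 to fall within 30 days of the last dose, the stop must be on or after day 2,044 − 30 = 2,014, which is week 2,014 / 7 = 287.7. If 801 is held 5 days early, the limit is (2,044 − 5 − 30) / 7 = week 287.0. For any earlier stop, 801 lies outside the AE period.

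**Step 3: the gap for earlier stops.** Gap in days = (292 − stop week) × 7.

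| Last dose at week | Days from last dose to Visit 801 |
|---|---|
| 52 | 1,680 |
| 104 | 1,316 |
| 208 | 588 |
| 284 | 56 |
| 288 | 28 |

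**Step 4: stops after week 288.** A patient in the extension who stops after week 292 has a nominal closeout date before the last dose, and no replacement date is given.

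**Step 5: other contacts.** The early-termination visit has no timing rule. If it is held on or before the last dose, a patient who leaves the study has no required contact in the following month. If it is held later, it may fall inside the month. A patient who stops drug but stays in the study keeps the regular visits, but after week 60 the next can be up to about 12 × 7 = 84 days away.

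**Step 6: the status of 801.** The Required row and footnote q give opposite answers on whether omitting it is a deviation. Steps 2 to 5 do not depend on how that is settled.

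**The case against.** The strongest reply is that the schedule is less bare than it first looks. The early-termination visit is required, records AEs, can be done by telephone and may fall inside the month. Section 4.9 separates stopping the product from leaving the study, so some patients keep their visits. SAEs must be collected for 28 days in any case. This all stands, and it rules out saying that the month has no contact for anyone. It does not supply a contact tied to the last dose.

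A reader might also infer several stronger points that the documents do not support.

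- *Visit 801 is plainly optional.* It is in the Required row. The evidence is a contradiction, read from a broken table, so the superscript needs checking.
- *Visit 801 precedes the last dose because of the taper.* Appendix 14 steps down "in two week increment unless resolution of AE requiring tapering". If a taper began at week 288, drug would end at 288 + 3 × 2 = week 294 or 288 + 4 × 2 = week 296. That path is an assumption. The synopsis caps treatment at 288 weeks outside the extension, and Appendix 14 is guidance for tolerance problems, not an end-of-study rule.
- *The blank diary cell at 801 is an omission.* The text in Section 1.5, "in the case of drug cessation, an additional 28 days of diary entries", describes the earlier expanded access program. Section 5.2.3 asks for diaries for at least two years from the start of treatment, so a blank at week 292 is consistent.
- *Under-collection is worst in patients who stop for toxicity.* These patients have added follow-up: repeat laboratory tests after tapering (Section 4.8), notice to the DSMB within 48 hours (Section 4.9) and the checks in Appendices 9 to 12.
- *Events counting toward the stopping rule will be missed.* The 28-day SAE duty applies regardless of cause, and many neurologic admissions are not SAEs under Section 8.4 at all. Missed events are not shown.

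**Conclusion.** The point holds in limited form. The plan states a one-month AE period and a 28-day SAE period after the last dose, and no required contact is timed to cover or close either. Visit 801 is correctly placed only for a stop at about week 288: its nominal date is within 30 days of the last dose only for stops at or after week 287.7, up to week 292. An early stopper who leaves the study, or a patient who stops in the extension, can pass the whole month without a required AE contact.

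The likely effect is under-collection of AEs in the withdrawal month. Its size cannot be given, because the documents do not say how many of the up to about 55 patients will stop drug or when. Patients who move to commercial supply continue on baricitinib and are outside the point.

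The conclusion rests on the week-292 anchor and the untimed early-termination visit. It does not need the footnote on 801 to be read correctly. This should be changed, but it does not touch the primary efficacy analysis.

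**What to change.** In Appendix 2:

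- Reconcile the row and the footnote so that Visit 801 is unambiguously required.
- Replace week 292 with a date counted from the actual last dose, at the end of the reporting period that Section 8.5 already states.
- Apply the visit to every patient who permanently stops drug, including early terminations and stops after week 288.
- Allow it by telephone, with AE collection.

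In Sections 8.5 and 8.5.1, reconcile the one-month, 30-day and 28-day periods, so that one contact can close them all or the differences are explained.

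Dosing and tapering rules are unchanged, and no diary requirement is added. The cost is table and footnote wording and one extra call per patient who stops. The downside is that a missed call becomes a deviation.
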